2. DESCRIPTION OF OBJECTIVES AND ENDPOINTS

2.1. Study Objectives

2.1.1. Primary Objective

The primary objective of the study is to evaluate the long-term safety of rFVIII Fc in subjects with hemophilia A.

2.1.2. Secondary Objective

The secondary objective of the study is to evaluate the efficacy of rFVIII Fc in the prevention and treatment of bleeding episodes in subjects with hemophilia A.

2.2. Study Endpoints

2.2.1. Primary Endpoint

The primary endpoint is the occurrence of inhibitor development.

2.2.2. Secondary Efficacy Endpoints

The secondary endpoints are as follows:

- The annualized number of bleeding episodes (spontaneous and traumatic) per subject
- The annualized number of spontaneous joint bleeding episodes per subject
- The total number of days of exposure per subject per year
- The consumption of rFVIII Fc as total dose per kg per subject per year
- Physician's global assessment of the subject's response to his treatment regimen using a 4-point scale
- Subject's assessment of response to the treatment of bleeding episodes using a 4-point scale

2.2.3. Major Surgery Endpoints

The major surgery endpoints are as follows:

- Investigator/Surgeon assessment of hemostatic response to surgery using the 4-point bleeding response scale
- Number of injections and dose per injection to maintain hemostasis during the surgical period
- Estimated blood loss (mL) during surgery and the post-operative period
- Number of blood product units transfused during surgery

2.2.4. Endpoints Based on Patient-reported Outcomes

Subjects will only take the questionnaires that they completed during the parent study. Subjects who go outside of the age range for a questionnaire should no longer complete the questionnaire. The Investigator will administer the age-appropriate questionnaire at the appropriate visits. The following patient-reported outcomes will be assessed.

Quality of Life (QoL) questionnaires:

- Haem-A-QoL
- Haemo-QoL
- Hemo-Sat-Patient Satisfaction Scale for parents/guardians, Version 15
- Canadian Hemophilia Outcomes-Kids' Life Assessment Tool (CHO-KLAT)
 - Children, Version 2.0 (for children previously enrolled in study 8HA02PED who are less than 18 years of age).
 - Proxy, Version 2.0p (for parents/guardians of children previously enrolled in study 8HA02PED and who are less than 18 years of age)
- EQ-5D Y (referred to as EQ-5D Youth for children in study 8HA02PED)
- EQ-5D-3L (referred to as EQ-5D in study 997HA301)

Health outcomes related to hemophilia will include:

- Number of hospitalizations excluding planned hospitalizations, elective surgery documented at Visit 1, and emergent surgery
- Number of emergency room visits
- Number of physician visits, excluding study visits
- Number of hospitalization days
- Number of days off work, school, day care, or preschool
- Number of days off work for the parent or caregiver

3. STUDY DESIGN

3.1. Overall Study Design and Plan

This is an open-label, multi-center, long-term study of IV administration of rFVIII Fc in previously treated patients (PTPs) with hemophilia A who have completed the A-LONG study (997HA301), the pediatric study (8HA02PED), or any other study with rFVIII Fc that plans to enroll subjects into this study after study completion or at a time specified in the protocol. This is a global study and will be offered to those countries participating in the parent studies.

Based on final and estimated sample sizes from these studies, approximately 214 subjects from studies 997HA301, 8HA02PED, 997HA307, and 997HA309 may be eligible to enroll in this extension study. The End of Treatment (EOT) Visit of the previous study may serve as the initial visit of the extension study. Assessments performed at this visit will be used to confirm eligibility for participation in the extension study.

Study visits are scheduled at 6-month (± 2 weeks) intervals following completion of Visit 1. Unscheduled visits may occur as deemed necessary by the Investigator. For subjects who undergo surgery, the Last Post-Operative Visit assessments will be performed when the subjects switch from their post-surgery dosing regimen to a regimen outlined in Section 3.2.1.

For subjects undergoing surgery, post-operative clinic visits may be more frequent. For subjects undergoing major surgery, a visit (Visit 3) is required 1-2 weeks after surgery (not required for minor surgery). A last post-operative visit (Visit 4) is required only if subjects who had major surgery did not return to a regular rFVIII Fc regimen as determined by the Investigator at Visit 3.

All subjects will have the opportunity to continue in this study for up to 4 years or until rFVIII Fc is commercially available in the applicable participating country.

Subjects first dosed with rFVIII Fc when <12 years of age in the parent study will be followed to at least 100 EDs in total across parent and extension study, even if rFVIII Fc becomes commercially available.

3.2. Treatment

Subjects 12 years of age or older will follow either a tailored prophylaxis, weekly prophylaxis, personalized prophylaxis, or episodic regimen based on the clinical profile of the subject and by the trough and/or peak (recovery) values, if needed, as observed in the parent study. Subjects are allowed to change treatment regimens (for example, from tailored prophylaxis to episodic, or from episodic to tailored prophylaxis) at scheduled or unscheduled visits during the study.

Subjects less than 12 years of age will receive 1 of 2 prophylactic regimens, tailored or personalized, and will not have the option to change to a weekly prophylactic or episodic regimen, unless they reach the age of 12 years during the study, at which time they can use any of the 4 treatment regimens. All regimen changes must occur at a scheduled or unscheduled clinic visit following assessment by the Investigator, and must be documented at that visit. Details (including date of change, new dose and/or dosing interval, and reasons for the change) will be recorded on electronic case report forms (eCRFs).

3.2.1. Regimens

3.2.1.1. Episodic Regimen

The individual dose of rFVIIIFc to treat bleeding episodes will be based on the subject's clinical condition, type and severity of the bleeding event, and if indicated, FVIII levels. A subject's PK profile and dosing levels from the parent study may also be used to guide dosing decisions. Subjects <12 years of age entering from another rFVIIIFc study will not be offered this option, but can receive an episodic regimen once they reach the age of 12 years during the study.

3.2.1.2. Prophylaxis Regimens

Details for each dosing option, including, if applicable, date of change, new dose and/or dosing interval, and reason(s) for the regimen change will be recorded on the appropriate eCRF each time a change is made.

Option 1: Tailored Prophylaxis

The Investigator may consider the following options for tailored prophylaxis to target a FVIII trough of up to 5%, but is encouraged to use the lowest effective dose targeting a FVIII trough level between 1% and 3%. If bleeding episodes occur at FVIII trough levels of 1% to 3%, further adjustments to dose or interval over the course of the study will target trough levels of up to 5%.

Dosing options are:

- approximately 25 IU/kg to 65 IU/kg every 3 to 5 days
- or dosing 2 times per week at approximately 20 IU/kg to 65 IU/kg on Day 1 and 40 IU/kg to 65 IU/kg on Day 4

The dose and interval should be based on the subject's clinical profile observed in the preceding rFVIIIFc study, and/or his individual PK (if available), and FVIII trough and/or peak (recovery) values.

In pediatric subjects, doses may be adjusted up to a maximum prophylactic dose of 80 IU/kg and the interval decreased to every 2 days, if necessary to maintain adequate FVIII activity trough levels and prevent spontaneous bleeding events.

Option 2: Weekly Prophylaxis

Dosing is approximately 65 IU/kg at weekly intervals. The dose should be based on the subject's clinical profile observed in the parent rFVIIIFc study, and/or his individual PK (if available), and FVIII trough and/or peak (recovery) values. Subjects <12 years of age at entry to 8HA01EXT will not be offered this option initially but may be prescribed this weekly prophylaxis regimen once they reach the age of 12 years during the study.

Option 3: Personalized Prophylaxis

If optimal prophylaxis dosing cannot be achieved using either of the above options, the Investigator may further personalize dosing to meet the needs of individual subjects.

The Investigator may consider the following personalized dosing options:

- Addition of "prevention" doses prior to strenuous activity

- Targeting a FVIII trough level of >3%, if the bleeding history and/or activity level requires
- Dosing less frequently

3.2.2. Surgery and Rehabilitation

If a subject requires emergent or elective surgery while participating in this study, he may be treated with the dose and regimen of rFVIII Fc deemed appropriate for the type of surgery. If a subject had a major surgery before the implementation of Protocol Amendment 2, only major surgeries that were not prescheduled were to be reported as SAEs. However, for subjects having a major surgery after the implementation of Protocol Amendment 2, all major surgeries were to be reported as SAEs.

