10.1.3. Surgery

For subjects who require emergent or elective surgery during the study period, the dose and regimen of rFVIII Fc shall be that deemed appropriate for the type of surgery to be performed.

All major surgeries must take place in a center that can provide study treatment, trained study personnel, post-operative assessments, and hematological consult by the Investigator or Co-Investigator. If the surgery does not occur in such a setting, the subject will be withdrawn from the study.

In addition, subjects who require major surgery may receive rFVIII Fc if

1. The surgery occurs within the contracted Institution for the trial and/or a separate agreement has been executed, permitting the use of study drug and Biogen Idec's rights to data generated in the trial at an alternative Institution deemed appropriate by the Principal Investigator.
2. The Investigator and/or appropriate qualified/licensed delegate is available to
 - a. Administer all rFVIII Fc doses required during surgery and during post-operative rehabilitation (if applicable).
 - b. Provide medical oversight and guidance throughout the duration of the pre-operative and the intra-operative periods.

Surgeries, elective or emergent, will be classified as major or minor, as follows:

- Major surgery is defined as any surgical procedure (elective or emergent) that usually, but not always, involves general anesthesia and/or respiratory assistance, in which a major body cavity is penetrated and exposed, or a substantial impairment of physical or physiological functions is produced (e.g., laparotomy, thoracotomy, craniotomy, joint replacement, or limb amputation).
- Minor surgery is defined as any surgical procedure (elective or emergent) that does not involve general anesthesia and/or respiratory assistance (e.g., minor dental extractions, incision, and drainage of abscess, joint or other injections, or simple excisions).

All major surgeries will be reported as SAEs.

Inhibitor testing should be performed 2 to 4 weeks prior to the scheduled surgery, pre-operatively on the day of surgery, 1-2 weeks post-surgery, and at the last post-operative visit (for minor surgery, testing is not performed at the last 2 timepoints). On the day of surgery, subjects will be given a pre-operative loading dose of rFVIII Fc as a bolus, and, in the case of emergency

CONFIDENTIAL

The information contained herein may not be used, disclosed, or published without the written consent of Biogen Idec MA Inc.

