15.1.3. Serious Adverse Event

An SAE is any untoward medical occurrence that at any dose:

- results in death
- in the view of the Investigator, places the subject at immediate risk of death (a life-threatening event); however, this does not include an event that, had it occurred in a more severe form, might have caused death
- requires inpatient hospitalization or prolongation of existing hospitalization
- results in persistent or significant disability/incapacity
- results in a congenital anomaly/birth defect

All major surgeries will be reported as SAEs. An SAE may also be any other medically important event that, in the opinion of the Investigator, may jeopardize the subject or may require intervention to prevent one of the other outcomes listed in the definition above. (Examples of such medical events include allergic bronchospasm requiring intensive treatment in

CONFIDENTIAL

The information contained herein may not be used, disclosed, or published without the written consent of Biogen Idec MA Inc.

an emergency room or convulsions occurring at home that do not require an inpatient hospitalization).

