8.2. Adverse Events

AEs will be classified using the Medical Dictionary for Regulatory Activities (MedDRA) system organ classes and preferred terms. MedDRA version 15.0 will be used throughout the study. All AEs will be listed.

In general, AEs will be analyzed based on *incidence*, defined as the proportion of subjects who had at least one occurrence of an event out of the number of subjects in the Safety Analysis Set.

All adverse event listings will include the onset and resolution study days relative to 8HA01EXT Study Day 1. AEs that are emergent during a major surgical/rehabilitation period, AEs that are emergent on the day of surgery and AEs that occur during the gap of greater than 7 or 4 days will be flagged. In addition, a separate listing will be provided for AEs that are emergent during a major surgical/rehabilitation period.

AEs occurring during a major surgical/rehabilitation period with an onset date on the day the surgical/rehabilitation period starts or on the day of the surgery will be included in the summaries of the study AEs but excluded from the summaries or listings of AEs occurring during a major surgical/rehabilitation period. Consideration is given to AEs with an onset date at the start of the surgical/rehabilitation period in the event the pre-surgical dose was administered the day before the surgery.

Events of overdose will not be included in the AE summary tables unless they are reported as adverse events.

The algorithm for the determination of AEs that are emergent during a major surgical/rehabilitation period, AEs with an onset date on the day of the surgical/rehabilitation period starts or on the day of the surgery, and AEs that are emergent during a treatment regimen period when an onset date is partially or completely missing is described below.

- If the onset date of an adverse event is present, then the date of onset will be compared with the start/stop dates of the major surgical/rehabilitation period and treatment regimen period to determine whether the adverse event is during a major surgical/rehabilitation

period, on the day of the surgical/rehabilitation period starts or on the day of the surgery, or during a treatment regimen period. If the onset of the adverse event is on the day of the treatment regimen change, then it will be attributed to the previous treatment regimen.

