8.2.6. Serious Adverse Events

Any AE reported as resulting in death, immediate risk of death (life threatening), inpatient hospitalization or prolongation of existing hospitalization, persistent or significant disability/incapacity, or a congenital/anomaly/birth defect will be classified as an SAE by the Investigator. An SAE may also be any other medically important event that, in the opinion of

the Investigator, may jeopardize the subject or may require intervention to prevent one of the other outcomes listed above.

All SAEs will be listed; treatment-emergent SAEs will be summarized by system organ class and preferred term.

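### Prescheduled major operations became reportable SAEs only at Protocol Amendment 2, yet the SAP plans a single SAE incidence across both reporting rules

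*SAP*

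**What the plan says.** SAP 3.2.2 describes two reporting rules within the same study. Before Amendment 2 was implemented, "only major surgeries that were not prescheduled were to be reported as SAEs". After it, "for subjects having a major surgery after the implementation of Protocol Amendment 2, all major surgeries were to be reported as SAEs". This is current SAP text about how the data were collected, not a change log. Protocol 15.1.3 carries the later rule without exception: "All major surgeries will be reported as SAEs". Protocol 10.1.3 counts elective as well as emergent procedures as major surgery.

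The analysis does not distinguish the two periods. SAP 8.2.6 plans that "All SAEs will be listed; treatment-emergent SAEs will be summarized by system organ class and preferred term". SAP 8.2.1 gives one overall count and percentage of subjects with a treatment-emergent SAE. SAP 8 sets the columns as parent study and overall, and the list of tables holds one SAE table.

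Two passages decide where an operation reported as an SAE will appear:

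- SAP 8.2: events in a major surgical/rehabilitation period whose onset is the day that period starts, or the day of surgery, "will be included in the summaries of the study AEs but excluded from the summaries or listings of AEs" tied to that period.
- SAP 8.2.1: events during major surgical/rehabilitation periods go into the surgery-subgroup column of the overall summary and into no other AE table. The exception in 8.2 is not repeated there.

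**The concern.** Long-term safety is the primary objective. The study has no control arm, and SAP 11 states that it has no independent data safety monitoring committee. Descriptive SAE percentages therefore carry much of the safety message.

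If the reporting rule changes during follow-up and the table pools across the change, the percentage depends partly on the calendar. Two subjects with identical, uncomplicated, prescheduled joint replacements would be classified differently only because one operation fell before the amendment and one after. The resulting figure follows neither definition throughout.

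**Working it through.** **1. Does the operation reach the main SAE table?**

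- *Is it treatment-emergent?* Yes. SAP 8.2.2 treats every AE on or after 8HA01EXT Study Day 1 as treatment-emergent.
- *What onset date would it carry?* The documents do not prescribe one. An SAE that is the operation itself would normally be dated on the day of surgery.
- *Under SAP 8.2:* an onset on the day of surgery or the period-start day keeps the event in the study AE summaries, so it enters the SAE table and the any-SAE and any-TEAE lines.
- *Under SAP 8.2.1 read alone:* the event appears only in the surgery-subgroup column of the overall summary. The two rules would still be mixed, but in that column only.
- *Dated after the day of surgery but within the period:* the event leaves the main tables under either passage.

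**2. How the two rules treat an uncomplicated major operation**

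| Operation | Before Amendment 2 | After Amendment 2 |
|---|---|---|
| Not prescheduled | SAE | SAE |
| Prescheduled | Not an SAE under this rule | SAE |

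Only the second row changes. It is not the same as all elective surgery: an elective operation that had not been prescheduled was reportable in both periods. Neither document defines prescheduled.

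**3. Denominator**

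SAP 3.3.1 gives planned parent-study sizes of 144, 50, 12 and 8. Their sum is 144 + 50 + 12 + 8 = 214, which reproduces the approximate figure in SAP 3.1. That figure is the number who may be eligible, so it only approximates the Safety Analysis Set.

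**4. Size per subject**

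Let *k* be the number of subjects whose only SAE is a prescheduled operation after the amendment, and *m* the number who would be in that position but had the operation before it. Compared with excluding such operations throughout:

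- the SAP's mixed rule adds *k*/214;
- counting all major operations throughout would add (*k* + *m*)/214.

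Neither *k* nor *m* is in the documents. SAP 7.6 describes the surgery subgroup as small, so I take a low range as an assumption:

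- *k* = 1: 1/214 = 0.47 points
- *k* = 2: 2/214 = 0.93 points
- *k* = 5: 5/214 = 2.34 points

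With *k* = *m* = 5, the mixed rule adds 2.3 points and a consistent all-operations rule would add 10/214 = 4.7 points, so the planned figure falls between the two consistent ones. The any-TEAE line moves only for subjects with no other TEAE, so its shift can be no larger.

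**The case against.** The strongest objection is that SAP 8.2.1 already removes events in major surgical/rehabilitation periods from every AE table except one column of the overall summary. It does not settle the matter, because SAP 8.2 makes an express exception for the dates an operation would normally carry. What stands is that the outcome depends on how the two passages are read together and on how sites dated the SAE.

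The SAP also discloses the rule change, tabulates SAEs by preferred term, flags surgery-day events in the AE listings and plans separate SAE and major-surgery listings. A careful reader could largely separate the operations by hand. That is true and limits the harm, but it does not correct the summary percentage.

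The planned analyses are descriptive, with no formal comparison. The inhibitor endpoint is untouched. The overall summary has its own lines for related TEAEs and related SAEs, which an operation judged unrelated would not enter. All of this stands.

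Two stronger readings are tempting. A reader might infer that the SAE percentage is greatly inflated, but no surgery or SAE counts are given and the subgroup is described as small. A reader might also infer that the parent-study columns cannot be compared because the groups spent different shares of follow-up under each rule. That is possible, but the documents give neither the implementation date of Amendment 2 nor entry dates by parent study, and SAP 5.1 presents the groups separately because their ages differ, not to compare them.

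**Conclusion.** The inconsistency is real and minor. The SAP states two SAE rules for prescheduled major surgery and plans one pooled incidence, so an uncomplicated prescheduled operation counts or not by date. On the natural reading of SAP 8.2 this affects the main SAE and TEAE summaries. If SAP 8.2.1 governs, it is confined to the surgery-subgroup column.

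The size is about 0.5 points per affected subject, or 0.9 to 2.3 points for an assumed 2 to 5 subjects. This rests on a denominator near 214, on the operation's SAE being dated on the surgery day or period-start day, and on those subjects having no other SAE. The true size cannot be computed from the documents. The correction is worth making because it is cheap and concerns a summary of the primary safety objective.

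**What to change.** - Keep SAEs as reported in the main table, so that it still matches the protocol's SAE definition.
- Add to the SAP 8.2.1 summary and the 8.2.6 table a supplementary SAE and TEAE incidence that applies one definition in both periods, excluding records that are solely a prescheduled major operation without a complication.
- State that admission for the planned operation does not count as a separate SAE criterion. Inpatient hospitalization is itself a criterion in Protocol 15.1.3, so without this statement the exclusion would catch few records.
- Define prescheduled before database lock. It is not among the surgery items in SAP 7.6. If the status was not captured, exclude every record that is only the operation itself, which also gives one rule throughout.
- Footnote the Amendment 2 implementation date and the number of major surgeries on each side of it.
- State whether SAP 8.2 or 8.2.1 governs surgery-day and period-start-day events.
- Keep all operations in the SAE listing and the surgery tables.

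The cost is SAP wording, one repeated table with an added summary line, and a review of the surgery SAE records already in the database. No data are lost and patients are unaffected.
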